#### 10.1.2 Safety Set

The Safety Set 1 includes all ICT naïve patients who received at least one dose of study medication during the core phase.

The Safety Set 2 includes all ICT pre-treated patients who received at least one dose of study medication during the core phase.

The Safety Set 3 includes all ICT pre-treated and naïve patients who received at least one dose of study medication during core phase.

The Safety Set 4 will consist of all patients who received at least one dose of granule formulation during the core or extension phase.

Patients will be analyzed according to the study treatment they actually received. A precise definition of “actually received” and of the analysis set used for pre-dose PK data analyses will be added in the SAP.

#### **10.1.3 Per protocol Set**

The Per Protocol Set consists of all ICT naïve patients from the FAS-1 without any major protocol deviation.

The protocol deviations that will lead to exclusion of patients from the PPS will be detailed in the SAP.

#### **10.1.4 Pharmacokinetic Analysis Set**

The Pharmacokinetic Analysis Set (PAS) consists of all patients who have at least one evaluable pre- or post-dose PK concentration (deferasirox).

A PK concentration is considered evaluable if it fulfills all of the following criteria:

- The actual dose or leading dose prior to pre-dose sampling must be as planned by protocol. In addition, the patient should have received the same dose during the last 4 days prior to sampling (except for Week 1 Day 1).
- The elapsed time between dose administration and PK concentration is documented.
- The PK concentration must NOT be associated with any vomiting within 4 hours of dosing.

### **10.2 Patient demographics/other baseline characteristics**

Demographic and other background data will be summarized descriptively by formulations and overall separately for the FAS-1, FAS-2 and the FAS-3.

Demographic data included age, age categories (2 to <10 years and 10 to <18 years), gender, race. Other background data included weight, weight group (<20 kg, 20-<35 kg, 35-<55 kg, 55-<75 kg, ≥75 kg), height, main underlying disease, history of splenectomy (Yes/No), prior iron chelation therapy (Yes/No), prior deferasirox (Yes/No), type of last chelation therapy prior to the study, hepatitis B and C status, medical history by MedDRA primary SOC and preferred term, abnormality in baseline ECG (Yes/No) and (clinically significant/non-significant), abnormality in baseline echocardiogram (Yes/No) and (clinically significant/non-significant), abnormality in baseline audiometric test (Yes/No) and (clinically significant/non-significant), abnormality in baseline ocular exam (Yes/No) and (clinically significant/non-significant, baseline creatinine, baseline creatinine group (≤upper limit of normal range (ULN), >ULN-≤1.5\*ULN and >1.5\*ULN), baseline creatinine clearance, baseline creatinine clearance group (<40, ≥40-<60, ≥60-<90 and ≥90 mL/min), baseline ALT, baseline ALT group (≤ULN, >ULN-≤3\*ULN, >3\*ULN-≤5\*ULN and >5\*ULN), baseline AST, baseline AST group (≤ULN, >ULN-≤3\*ULN, >3\*ULN-≤5\*ULN and >5\*ULN), urine protein/creatinine ratio (≤0.2 mg/mg, >0.2-≤0.5, >0.5-≤1 mg/mg and >1 mg/mg), baseline serum ferritin and baseline serum ferritin group (<1000, ≥1000 to ≤2500, >2500 to ≤5000, >5000 ng/mL).

Categorical data will be presented as frequencies and percentages. For continuous data, mean, standard deviation, median, 25th and 75th percentiles, minimum, and maximum will be presented.

### **10.3 Treatments (duration of exposure, concomitant therapies, percentage of planned dose taken)**

The following variables will be summarized with descriptive measures separately for the Safety Set-1, Safety Set-2, Safety Set-3 and Safety Set-4 by formulation: duration of exposure, in weeks and in categories (core phase: <4 weeks, 4-<12 weeks, 12-<20 weeks, 20-<28 weeks, 28-<36 weeks, 36-<44 weeks,  $\geq$ 44 weeks and extension phase: <6 months, 6-<12 months, 12-<24 months, 24-<36 months, 36-<48 months,  $>$ 48 months); average planned (mg/kg/day) and average actual daily dose; cumulative planned (mg/kg) and total actual dose (mg/kg); percentage of planned dose taken; frequency of interruptions, decreases and increases in planned dose, overall and by reason for change as recorded in the eCRF.

The total patient-years while on treatment, calculated as the sum of (overall drug exposure) / 365.25 will be provided by formulation.

The duration of exposure, defined as the number of weeks (core phase) / months (extension phase) between the start and end of study medication, will be summarized by formulation and by phase. The end of study medication day is the last day with a non-zero actual dose of study medication as recorded on the drug administration pages.

The average daily dose (planned or actual, in mg/kg) is calculated as the mean dose over all days between first and last dose, excluding interim days with zero dose (interruptions). The cumulative dose is calculated as the sum over the daily doses of all days between first and last dose. The current weight is used when calculating the actual daily dose.

The percentage of planned dose taken is derived as  $100 * \text{cumulative actual dose (mg/kg)}/\text{cumulative planned dose (mg/kg)}$ .

Prior and concomitant medications and significant non-drug therapies will be summarized through frequency tables according to their WHO ATC class and WHO generic term by phase. Prior medications are defined to be drugs taken prior to the first dose of study medication. Concomitant medications are medications taken between the first day of study medication and up to 30 days after the last day with study medication or medications starting prior to the first day of study medication and continuing after the start date of study medication.

### **10.4 Primary objective**

The primary objective of this study is to evaluate patient compliance with study treatment, as measured by the count of deferasirox granules stick packs/dispersible tablets and to evaluate the change in serum ferritin over time for both formulations of deferasirox in pediatric ICT naive patients with iron overload during core phase, after 24 weeks of treatment.

#### **10.4.1 Variables and analysis set**

All analyses for the primary objective will be performed on the FAS-1 and presented by treatment group: deferasirox DT and deferasirox granule formulation.

The co-primary efficacy variables are:

- Compliance measured by stick pack /tablet count based on amount of medication dispensed, returned and reported as lost/wasted by the patient or caregiver, over 24 weeks of treatment (i.e. assessed at week 25 visit). Compliance will be calculated as the ratio of total count consumed to total count prescribed, where
  - total count consumed is derived from cumulative dispensed, returned and lost/wasted counts over 24 weeks of treatment (i.e. assessed at week 25 visit);
  - total count prescribed is cumulative prescribed count over 24 weeks of treatment (i.e. assessed at week 25 visit).
- Change from baseline in serum ferritin after 24 weeks of treatment (i.e. assessed at the week 25 visit).

#### **10.4.2 Statistical method of analysis**

The primary efficacy analysis will be the comparison of means between the two treatment arms of change from baseline after 24 weeks of treatment in SF and mean relative consumed stick pack /tablet count over 24 weeks of treatment.

The trial will be claimed successful if the superiority of granule formulation relative to DT formulation could be demonstrated with regard to both endpoints. Therefore, no adjustment for multiplicity of the type I error (alpha) is required.

The primary inferential analysis described below will be based on the FAS-1.

Let  $\mu_{SF,G}$  and  $\mu_{SF,DT}$  denote the mean change from baseline in SF to week 25 visit for granule and DT formulations, respectively. Let  $\mu_{C,G}$  and  $\mu_{C,DT}$  be similarly defined for compliance measured by stick pack /tablet count.

The null and the alternative hypothesis are defined as follows:

$H_0,SF: \mu_{SF,G} = \mu_{SF,DT}$  no effect of granule formulation with regard to change in SF, and/or

$H_0,C: \mu_{C,G} = \mu_{C,DT}$  no effect of granule formulation with regard to compliance

versus

$H_1,SF: \mu_{SF,G} < \mu_{SF,DT}$  mean change in SF favorable for granule formulation compared to DT formulation, and

$H_1,C: \mu_{C,G} > \mu_{C,DT}$  mean compliance favorable for granule formulation compared to DT formulation

Analysis of covariance (ANCOVA) will be performed for comparison between both treatment groups. The ANCOVA model for compliance endpoint will include treatment group and age group (2 to <10 years, 10 to <18 years) as factors. The model for serum ferritin endpoint will also include the serum ferritin value at baseline as covariate.

For each of the endpoint the following estimates from the ANCOVA will be provided:

- the least squares mean with 2-sided 95% confidence interval for each treatment arm
- the least squares means with 2-sided 95% confidence interval, p-value for the difference between treatment arms

#### **10.4.3 Handling of missing values/discontinuations**

In case of missing serum ferritin value after 24 weeks of treatment, the last available post-baseline serum ferritin value will be used in the calculation of the primary endpoint. Patients without post-baseline serum ferritin value will be excluded from the analysis.

#### **10.4.4 Supportive analyses**

The following supportive and supplementary analyses will be provided:

- The primary analysis will be repeated for the FAS-2 and FAS-3.
- The primary analysis will also be provided for the PPS;
- If more than 10% of patients have no serum ferritin value after 24 weeks of treatment, supplementary analyses will be performed for the primary analysis for serum ferritin using imputation techniques. Details will be provided in the study SAP.

Other supportive analyses may be detailed in the SAP.

### **10.5 Secondary objectives**

#### **10.5.1 To evaluate both formulations on change in serum ferritin and compliance measured by stick pack /tablet count after 48 weeks of treatment in ICT naïve patients**

Descriptive analyses will be performed after 48 weeks of treatment for the FAS-1. Absolute and relative change from baseline in serum ferritin for core phase will be summarized after 48 weeks of treatment using standard descriptive statistics by treatment arm.

In addition at the time of primary analysis if more than 10% of patients have no serum ferritin value after 48 weeks of treatment or missing compliance measured by stick pack/tablet count over 48 weeks of treatment, a supplementary analysis will be performed using multiple imputation method. Details will be provided in the study SAP.

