## Amendment 5 (06-Dec-2017)

### Amendment rationale

As of 06-Dec-2017, 210 patients have been randomized (94 chelation naïve and 116 pre-treated patients). The pre-treatment arm is fully accrued.

The purpose of this amendment is to modify the assessment timepoint for the primary analysis (currently change from baseline for serum ferritin and compliance after 48 weeks of treatment), and to reduce the sample size for the chelation naive patients , following recent interaction with Health Authorities. The eligibility criteria for the extension phase have been modified.

Amendment rationales are as follows:

1. The assessment timepoint for the primary analysis will be modified for serum ferritin and compliance to 24 weeks of treatment (as assessed at week 25 visit), in lieu of 48 weeks. A linear relationship between changes from baseline at 24 and 48 weeks of treatment has been established based on a pool of representative randomized studies (CICL670A0105, CICL670A0107, CICL670A0109 and CICL670A2206) with serum ferritin available at 6 and 12 months for deferoxamine and deferasirox arms. The model fits well in the set of observations and showed that the treatment effect at 6 and 12 months are correlated, with a slightly more pronounced effect at 12 months. This finding supports the use of the 6 months time-point as reliable surrogate for the 12 months time-point (Novartis data on file). Primary endpoints based on changes from baseline after 24 weeks of treatment will allow an earlier disclosure of primary analysis. The compliance (using drug count) has been evaluated in pediatric patients over 6 months and 12 months for deferoxamine and deferasirox arms in the ICL670A2206 study. The observed treatment effect over 6 months vs. 12 months is similar. This suggests compliance over 6 months is accurate at predicting compliance over 12 months. Furthermore data comparing deferoxamine and deferasirox suggest a self-reported adherence to deferasirox DT of 97% after one year. Therefore it can be assumed that the 6 month reported adherence will be very similar and can serve as a surrogate (Trachtenberg 2011)The rationale is also based on the demonstrated relationship of efficacy as assessed by serum ferritin with deferasirox dose, iron burden and continuous iron intake (Cappellini et al 2006).

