**Figure 4-1**      **Study schema**

## **4.2 Timing of interim analyses and design adaptations**

One interim analysis has been added to allow for early analysis of the data if requested by the health authority. All the analyses included in the interim analysis will be descriptive. The IA will be performed by the Novartis study team. No decisions regarding the future course of the trial is anticipated at the time of the IA and the trial will continue.

All patients randomized in the study and who have completed a minimum of 12 weeks of treatment exposure or discontinued from treatment core phase at the time of the cut-off date will be included in the interim analysis (Section 10.7).

The cut-off for the primary analysis will be 24 weeks after approximately 96 ICT naive patients have been randomized.

The core data analysis is planned when all patients have completed their 48 week study treatment in the core phase including safety follow-up (if applicable).

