## **1 Introduction**

This document details the planned statistical analysis for data collected during the core and extension phases in the study CICL670F2202. The SAP from the primary analysis (CSR SAP Amendment 3, dated 26Mar2018) will be used as a reference for this SAP. The CSR SAP is located at the following CREDI location:

Clinical Study Report (CSR) deliverables (tables, figures, listings - TFLs) and further programming specifications are described in separate documents namely TFL Shells and Programming Datasets Specifications (PDS), respectively. An interim and the primary analysis were performed in the study. The data cut-off date for the interim analysis was 16-Nov-2017 and included all randomized ICT naïve patients who had completed a minimum of 12 weeks of treatment exposure or discontinued from the treatment core phase by the cut-off date. The primary analysis was performed when 96 randomized ICT naïve patients had completed 24 weeks of treatment or discontinued early (data cut-off date: 31-May-2018). All data collected within the core phase of the study at the time of the primary data cut-off date were reported in the primary analysis CSR.

This analysis plan describes the analyses for an End of Core Phase (EoC) CSR requested by the CHMP that will include the cumulative data from the completed core phase and extension phase with a data cut-off date of 18-Jan-2021. This data cut-off date allows the inclusion of all patients who have completed a minimum of 3 years of treatment or discontinued from treatment in the core or extension phase. Only the analyses based on the core and extension phase described in this analysis plan will be performed for this EoC phase CSR. Analyses that were presented in the primary CSR and for which no additional data was collected after the primary analysis data cut-off date (e.g. baseline demographics) will not be repeated for the EoC phase analysis.

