#### **2.9.3    Changes from baseline in serum ferritin after 48 weeks of treatment during core phase**

Summary of absolute and relative change from baseline values in serum ferritin assessed at week 48 visit and 95% confidence intervals for means (see [Table 4-2](#) for time window definition) will be provided for FAS-1, FAS-2 and FAS-3.

Furthermore, a graphical presentation of mean and standard deviation of absolute value in serum ferritin will be plotted by treatment arm and time-window (see [Table 4-2](#) for time-window definition) for FAS-1, FAS-2 and FAS-3.

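### The 48-week multiple imputation is tied to a cut-off by which roughly a third of naive patients could not have reached week 48; the complete 48-week data get neither imputation nor a covariate-adjusted comparison

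*Protocol*

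**What the plan says.** Amendment 5 (06-Dec-2017) moved the primary time point. It describes the endpoint it replaces as "currently change from baseline for serum ferritin and compliance after 48 weeks of treatment" and states: "The assessment timepoint for the primary analysis will be modified for serum ferritin and compliance to 24 weeks of treatment".

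For week 48 in naive patients, Protocol 10.5.1 now says: "Descriptive analyses will be performed after 48 weeks of treatment for the FAS-1". It adds a supplementary multiple imputation with this trigger: "In addition at the time of primary analysis if more than 10% of patients have no serum ferritin value after 48 weeks of treatment". A parallel trigger covers missing 48-week compliance. Protocol 4.2 fixes the primary analysis date: "The cut-off for the primary analysis will be 24 weeks after approximately 96 ICT naive patients have been randomized". SAP 2.1 (the SAP for the primary analysis) excludes any data collected after the cut-off.

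SAP 2.8.5 repeats the 48-week imputation with the same 10% threshold but does not say at which analysis it applies. SAP 4.6.1 describes imputation for week 24 only.

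The End of Core SAP covers the completed core phase. Its section 2.9.3 plans this for FAS-1, FAS-2 and FAS-3: "Summary of absolute and relative change from baseline values in serum ferritin assessed at week 48 visit and 95% confidence intervals for means". Section 2.9.1 does the same for compliance. Section 2.8.2 repeats the ANCOVA for the 24-week variables only. The introduction limits the scope: "Only the analyses based on the core and extension phase described in this analysis plan will be performed for this EoC phase CSR". No imputation is listed.

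**The concern.** Imputation is meant to show whether dropout could change the 48-week result. Placed at a cut-off 24 weeks after the last naive randomisation, it would mostly fill in visits that had not yet fallen due. When all patients have finished the core phase and the only missing values are genuine ones, no imputation is planned.

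The second gap is the comparison itself. Week 48 was the primary time point for most of the trial, and the case for moving to week 24 is that it stands in well for week 48. An age- and baseline-adjusted difference at 48 weeks from this trial would be the direct check. The model is already written and is rerun in the End of Core report, but only at 24 weeks.

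**Working it through.** The documents give no figure for the share of naive patients who could have reached week 48 by the primary cut-off, so it has to be derived from dates and counts. They do state a 48-week precision, which step 6 reproduces.

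1. **Latest useful randomisation date.** The cut-off was 31-May-2018 (Protocol, Amendment 6 rationale). In SAP Table 4-2 the week-49 window has k = 11, so the planned day is (5 + 4×11 − 1)×7 + 1 = 337, and the window opens on day 337 − 14 = 323. Reaching day 337 by the cut-off needs randomisation by 31-May-2018 − 336 days = 29-Jun-2017. Reaching day 323 needs 31-May-2018 − 322 days = 13-Jul-2017.

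2. **Naive patients in by those dates.** There were 60 on 15-Jun-2017 (Amendment 4) and 94 on 06-Dec-2017 (Amendment 5), 174 days apart. Assuming linear accrual:
   - Day 337: 60 + 14×34/174 = 62.7; 96 − 62.7 = 33.3 short (34.7%).
   - Day 323: 60 + 28×34/174 = 65.5; 30.5 short (31.8%).

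   Between the two dates total randomisations rose by only 32 (178 to 210) and the pre-treated count fell from 118 to 116, so two patients were probably reclassified. Treating them as naive throughout:
   - Day 337: 62 + 14×32/174 = 64.6; 31.4 short (32.7%).
   - Day 323: 62 + 28×32/174 = 67.1; 28.9 short (30.1%).

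   Ceiling: the 60 counted on 15-Jun-2017 entered at least 350 days before the cut-off. If none of the other 36 could reach week 48, the share is 36/96 = 37.5%.

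3. **Against the trigger.** 10% of 96 is 9.6, so ten patients without a value are enough. To stay below it, 87 patients would have to be in by 29-Jun-2017. That is 27 entries in 14 days, when 34 entered over 174 days.

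4. **Check on linearity.** SAP 2.12 expects about 74% of patients at the interim. Twelve weeks of exposure by 16-Nov-2017 means randomisation by 25-Aug-2017, 71 days after 15-Jun-2017.
   - If 74% refers to 96 patients: 0.74×96 = 71, so 25 (26%) entered later still and certainly could not reach week 48.
   - If it refers to the 120 still shown in SAP 1.1: 0.74×120 = 88.8. Then 60 + 14×28.8/71 = 65.7, leaving 30.3 (31.6%) at day 337, and 60 + 28×28.8/71 = 71.4, leaving 24.6 (25.6%) at day 323.

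   Each result is more than twice the trigger.

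5. **Complete core data.** All patients had finished the core phase by 18-Dec-2018 (Amendment 6 rationale). Missing values due to visits not yet reached are then zero and only dropout remains. The sample-size section assumes 5%.

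6. **What adjustment could add.** Protocol Table 10-3 gives a half-width of 303.6 for 60 patients. This implies SD = 303.6×√60/1.96 ≈ 1200, and 1.96×1200/√60 = 303.6 reproduces it. The 45-patient row (350.6) gives an unadjusted between-arm half-width of √2×350.6 ≈ 496 ng/mL. Adjustment multiplies this by √(1 − ρ²), where ρ is the covariates' correlation with the change: 473, 429 and 354 ng/mL for ρ = 0.3, 0.5 and 0.7. These ρ values are assumed, as is carrying this SD over to naive patients.

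**The case against.** Several points on the other side have force.

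- **The tie to the primary cut-off is in the Protocol only.** SAP 2.8.5 drops it, and the SAP introduction still places the primary report at the end of the core phase. This stands as a reason to call the documents inconsistent. But SAP 2.1 and the actual cut-off follow the 24-week rule, and no later SAP moves the imputation to the complete data. The End of Core SAP's general reference back to the earlier SAP does not override its own limit on scope.
- **Missingness caused only by a late entry date is where missing-at-random is most plausible.** That is true, and an early imputed 48-week estimate would not be invalid. It would just say little about dropout.
- **On the complete data the trigger might not fire**, since assumed dropout is 5%. That is also true, and no document gives the actual 48-week dropout. A trigger that stays silent because few values are missing is working as intended.

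A reader might also infer three stronger things that the documents do not support.

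- **That there is no between-arm information at 48 weeks.** Protocol 10.5.2 plans a forest plot of ferritin change at 24 and 48 weeks. It names no covariates, SAP 2.8.4 defines its forest plot at 24 weeks, and the End of Core SAP has none. Even so, an unadjusted difference follows from the per-arm means and intervals.
- **That End of Core SAP Table 3-1 hides a departure on the imputation.** The Protocol places that imputation at the primary analysis, so leaving it out at End of Core changes nothing the Protocol specified.
- **That interim results prompted the switch to 24 weeks.** The End of Core SAP says: "The data cut-off date for the interim analysis was 16-Nov-2017". Amendment 5 followed 20 days later, but a cut-off date is not a date of results. The SAP version adding the interim is dated 08-Dec-2017, two days after the amendment. The interim was descriptive. Amendment 5 cites slow recruitment, health-authority discussions, and pooled data showing a slightly larger effect at 12 months. The End of Core SAP records that the primary objective was not met, so no positive claim rests on the change.

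**Conclusion.** The point holds as a low-cost improvement. Under Protocol 10.5.1 the 48-week imputation would be triggered by incomplete follow-up alone. About 30% to 35% of naive patients could not have reached week 48 at the primary cut-off, with a ceiling of 37.5%, against a 10% threshold. The range rests on linear accrual between two documented counts and is not a reported figure. That the threshold is exceeded does not depend on linearity, because avoiding it would need 27 entries in two weeks.

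The complete 48-week data have no planned imputation and no covariate-adjusted between-arm estimate. What is missing is precision and a dropout check on the former primary endpoint, not the comparison as such. The possible gain in precision depends on a covariate correlation the documents do not give.

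**What to change.** In Protocol 10.5.1 and SAP 2.8.5, apply the 48-week imputation trigger to the complete core data, counting as missing only patients whose planned week-49 visit date has passed. State the 48-week imputation model, since SAP 4.6.1 covers week 24 only.

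In End of Core SAP 2.9.1 and 2.9.3, add the section 2.8.2 ANCOVA for 48-week compliance and 48-week ferritin change in FAS-1, reporting the least-squares mean difference with its 95% confidence interval. Label it supportive and identify it as the primary time point before Amendment 5.

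The primary analysis was completed on 07-Dec-2018, and the final-report SAP records the End of Core report as done. Anything run after reporting must therefore be labelled post hoc. The cost is some SAP wording and a few supportive model runs on data already collected, with no alpha spent.
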